**Background and Purpose:**

Our long-term goal is to demonstrate the effects of acupuncture for the treatment of vulvodynia. Up to 14 million American women have vulvodynia, a debilitating pain syndrome characterized by pain (burning, irritation, stinging or rawness) in the vulva and dyspareunia that renders sexual intercourse virtually impossible and leaves these women desperate for relief. Not only are women in pain, but they often lose their partners or have relationship difficulties due to their inability to have sexual intercourse. No therapies have been proven efficacious and rapid pain relief is unpredictable and rarely possible. After exhausting Western Medicine options, these women often turn to acupuncture. But in contrast to other pain conditions, there have been no acupuncture sham control studies of vulvodynia.

Only four studies, including one of ours, provide some evidence of the effect of acupuncture on vulvodynia. In three, single-group acupuncture studies, women had less pain, better quality of life, improved sexual health, and improved mental health. Our randomized wait-list controlled pilot study of 36 women with vulvodynia showed great promise. We found a statistically significant and clinically meaningful reduction in vulvar pain and dyspareunia, and an increase in overall sexual function after a 5-week, 13-needle, 10 session acupuncture protocol. This newly developed, standardized acupuncture treatment protocol is the first breakthrough in the treatment of this puzzling disorder. It includes acupuncture points that relieve pain in the genitals. The results of our initial pilot study provided the first evidence from a two-group design that the acupuncture protocol could reduce pain intensity, pain during intercourse, and increase overall sexual function. Our findings, however, warrant stronger evidence to support the inference that the effect is indeed due to the acupuncture since ours or no other study included a sham control or provided follow-up data beyond immediate posttest, which means that the duration of the acupuncture effect is unknown. Our recent feasibility study paves the way to overcome this gap by use of double-blind acupuncture needles. Findings from these two studies support our proposal for the world's first double-blind randomized controlled trial (RCT) of acupuncture for vulvodynia while exploring its duration of effect.

We will conduct a phase 2 double-blind, pretest/posttest RCT to compare effects of penetrating needles or the skin touch placebo needles on vulvar pain in our 13-needle, 10-session acupuncture treatment protocol. A sample of up to 130 women, with a diagnosis of vulvodynia, either generalized or provoked vestibulodynia, will be recruited. Subjects will be stratified by type of vulvodynia, and will be randomized 1:1 either to the penetrating needle group or the skin touch placebo needle group. These double-blind needles will provide a strong sham procedure (placebo) to mask both the acupuncturist and subject to the type of needle used for the 10-treatment protocol.

**Title: DOUBLE-BLIND PHASE 2 RCT: EFFECT OF ACUPUNCTURE ON PATIENT VULVODYNIA OUTCOMES**

**RESEARCH PROTOCOL**

Dated 8/15/2017

Specific aims are to:

Aim 1. Compare the penetrating needle group and the skin touch placebo needle group for effects on the: (a) primary outcome: vulvar pain (PAINReportIt® average pain intensity, 0-10), and (b) secondary outcomes: dyspareunia (FSFI dyspareunia) and sexual function (FSFI total). We hypothesize that controlling for baseline values, at posttest there will be statistically significant less vulvar pain (primary) and dyspareunia and better sexual function in the penetrating needle group compared to the skin touch placebo group.

Aim 2. In subjects with a clinically meaningful reduction in pain intensity (at least 1.5 points) at posttest compared to pretest, describe the duration of the acupuncture treatment and placebo effects weekly until pain returns to pretest or up to 12 weeks after posttest. We will describe the variability over time in vulvar pain intensity (0-10) after a tampon insertion-removal stimulus and thereby explore the duration of the effect by intervention group, vulvodynia subgroups, and demographic subgroups (e.g., age, race, occupation). These findings will provide insights to guide future research on initial and maintenance acupuncture for vulvodynia.

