**Study design:**

We will conduct a pretest/posttest, randomized, placebo controlled phase 2 efficacy study on 130 subjects with vulvodynia, with high scientific rigor. In this adequately powered study, we will compare two groups (penetrating acupuncture needle [treatment] group and skin touch needle [placebo] group) in a 13-needle, 10-session acupuncture protocol delivered twice/week for 5 weeks for effects on vulvar pain (primary outcome), and dyspareunia and sexual function (secondary outcomes). Subjects will be stratified by type of vulvodynia (generalized or provoked) and randomized 1:1 either to the penetrating needle group or the skin touch placebo needle group. These double-blind needles will provide a strong

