**Subject identification, recruitment and consent:**

The subjects will be women with a diagnosis of vulvodynia, who are 18 – 45 years of age. Potential participants will be recruited from clinical and community settings in Chicago, such as the UIC campus and surrounding communities, gynecologists, certified nurse-midwives, family physicians, and women's health physical therapy practices. Recruitment will also be conducted via a link on the National Vulvodynia Association (NVA) website. We will also recruit through social media like Facebook, in addition to through phone calls and emails. We plan on recruiting up to 130 women to ensure that we have full data on 80 subjects after screening and attrition. We will strive to enroll a racially and ethnically diverse sample of women.

The consent process will be completed at the UIC College of Nursing. It may also be completed at another UIC or other private location chosen by the potential subject to go over the details of the study and informed consent. All study procedures will be conducted at the UIC College of Nursing in fully equipped, clinical research exam rooms on the second floor. The screening gynecological screening exam will take place in one of the exam rooms in the CON or at [name] office in the UIC hospital.

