**Procedures:**

The research specialist (RS) will determine initial eligibility by screening potential participants during an initial telephone or in-person interview according to the inclusion and exclusion criteria. Women deemed to be eligible and interested in participating will be scheduled to go over the consent process and will then receive a gynecological screening exam by [name], a urogynecologist with expertise in changes in pelvic floor tissue related to vulvodynia, or [name], a practicing certified nurse-midwife with over 29 years of experience and a practicing acupuncturist specializing in the treatment of vulvodynia patients for 15 years. This exam will confirm the diagnosis and subtype of vulvodynia (provoked or generalized). Potential participants will also be asked to insert and remove a tampon as a standardized stimulus to provoke vulvodynia pain and women will be eligible if they report a pain level of 4 or higher. We will always use a regular size Tampax™ tampon with applicator as part of the standardized procedure. Participants determined to be ineligible after the above steps will not be able to continue study participation.

Based on the gynecological exam results, participants will be assigned to the generalized or to the provoked vulvodynia group. Eligible women will be able to start the study procedures immediately or at a future visit. Right before the first acupuncture session and once a week before an acupuncture treatment, a urine pregnancy test will be administered. If it is positive, the subject will be discontinued from the study.

Participants will be assigned at random to the experimental group, who will be treated with penetrating needles, or the control group, where the needles have a blunt tip that pinches but does not penetrate the skin. The special needles used in this study are inside an opaque insertion tube so that both the acupuncturist and participant remain blind to group assignment. The actual acupuncture needles,

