**Sample size:**

We plan to recruit 130 women to ensure that we obtain full data for 80 subjects.

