**Data analysis:**

[name] will supervise all data analysis procedures. Prior to data collection and entry, a codebook will be created with the variable names, descriptions, and value codes of each variable. Missing data will be minimized through our retention efforts but are inevitable, to some degree, in any longitudinal study. We will address missing data by intention to treat analyses (ITT), using the full information maximum likelihood (FIML) approach, which has been shown to produce unbiased parameter estimates and standard errors. To begin to phenotype subjects with emotional disturbances we will explore the emotional dimension of pain at baseline and after the 10th acupuncture treatment using the well-known Pain Rating Index-Affective (PRI-A) score from PAINReportIT®.

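### Randomisation is stratified by vulvodynia type, but the Aim 1 comparison adjusts only for baseline; adding type would recover power at almost no cost

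*Combined protocol and SAP*

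**What the plan says.** - **Allocation (Study design; Background and Purpose says the same).** "Subjects will be stratified by type of vulvodynia (generalized or provoked) and randomized 1:1".
- **Aim 1 comparison (Specific aims).** "We hypothesize that controlling for baseline values, at posttest there will be statistically significant less vulvar pain". The same sentence goes on to the two secondary outcomes, dyspareunia and sexual function. Baseline is the only adjustment named, and it appears in a hypothesis rather than in a model.
- **Data analysis.** "We will address missing data by intention to treat analyses (ITT), using the full information maximum likelihood (FIML) approach". The section gives no primary model, covariate list or stratum term.
- **Use of type in an analysis.** It appears only in Aim 2, which will "explore the duration of the effect by intervention group, vulvodynia subgroups, and demographic subgroups". That use is descriptive.
- **Size (Sample size).** "We plan to recruit 130 women to ensure that we obtain full data for 80 subjects".
- **Availability of type (Procedures).** The gynecological screening exam confirms the subtype before randomisation, so it should be known for every randomised woman.

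**The concern.** A plan followed as written would stratify on type and then compare the groups without it. If type carries prognostic information beyond the baseline score, two things can follow.

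- **Allocation balanced within type.** The treatment estimate already benefits from the balance. A model without type still counts the type differences as noise, so the reported standard error is too large and the test is conservative.
- **Allocation not balanced within type.** The standard error is honest, but the estimate itself is noisier than it need be.

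Either way power is lost, in a trial that aims for full data on only 80 women. There is also a lesser point. If the stratum term is not named in advance, the choice between adjusted and unadjusted results stays open until the data have been seen.

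**Working it through.** **What can be reproduced.** The target of 80 cannot. The documents give no alpha, power, between-group difference or SD. Going from 130 to 80 is a loss of 50/130 = 38.5%, but no loss rate is stated to compare it with.

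**Inputs.** From the documents: 80 women with full data, 1:1 allocation, two types. Assumed: two-sided alpha 0.05, two types of equal size, residual variance given baseline set to 1 (so no SD is needed), and r, the share of that variance explained by type, equal to 0, 0.05, 0.10 or 0.15.

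**Closed form: type omitted, exact balance within type, adjusted model set at 80% power.**

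- SE inflation = 1/√(1−r) − 1
- Type I error = 2[1 − Φ(1.96/√(1−r))]
- Power = 1 − Φ(1.96/√(1−r) − 2.80)
- Equivalent women lost = 80 − 80[(z_power + 1.96)/2.80]²

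At r = 0.10, for example, 1/√0.90 = 1.054 and 1.96 × 1.054 = 2.066. Type I error is 2[1 − Φ(2.066)] = 3.9%, and power is 1 − Φ(2.066 − 2.80) = 76.9%.

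| r | SE inflation | Type I error | Power | Equivalent women lost |
|---|---|---|---|---|
| 0 | 0% | 5.0% | 80% | 0 |
| 0.05 | 2.6% | 4.4% | 78.5% | 2.9 |
| 0.10 | 5.4% | 3.9% | 76.9% | 5.9 |
| 0.15 | 8.5% | 3.4% | 75.0% | 9.2 |

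**Dependence on allocation.** The documents do not say whether allocation is blocked within type, so three cases were simulated. Each used the ANCOVA t-test with and without type, N = 80 and 20,000 replicates per cell (Monte Carlo SE about 0.15 points for type I error and 0.3 for power). The effect was 2.80 × √(1−r) × 2/√80, which gives about 78% adjusted power with the t-test. The dropout case takes 128 balanced women down to 80 at random. That is an upper bound, because the protocol's allowance also covers women lost at screening.

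Type I error without type:

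| r | Exact balance | After dropout | No blocking |
|---|---|---|---|
| 0 | 5.0% | 5.1% | 4.8% |
| 0.05 | 4.5% | 4.9% | 5.0% |
| 0.10 | 4.0% | 4.4% | 5.0% |
| 0.15 | 3.4% | 3.7% | 4.9% |

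Power without type / with type:

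| r | Exact balance | After dropout | No blocking |
|---|---|---|---|
| 0 | 77.9 / 77.9 | 78.3 / 78.1 | 77.9 / 77.4 |
| 0.05 | 76.5 / 78.0 | 76.4 / 77.9 | 76.1 / 77.6 |
| 0.10 | 75.1 / 78.4 | 74.2 / 77.6 | 73.9 / 77.9 |
| 0.15 | 73.2 / 78.7 | 72.4 / 77.9 | 71.3 / 77.5 |

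The conservatism shrinks with dropout and vanishes without blocking. The power gain from adding type does not: it is about 1.5 points at r = 0.05, 3.3 to 4.0 at 0.10 and 5.5 to 6.2 at 0.15. At r = 0, adding type changes power by 0 to −0.5 points.

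**A different anchor.** Suppose instead that the baseline-only comparison has 80% power by the usual formula (difference d = 2.80 × √(2/40) = 0.626 residual SD). With k = √(2/40), power with type is Φ(d/(k√(1−r)) − 1.96), and without it, under balance, Φ((d − 1.96k)/(k√(1−r))). Without versus with type this gives 80.6% vs 82.0% at r = 0.05, 81.3% vs 84.0% at 0.10 and 81.9% vs 86.0% at 0.15. The gap is about 1.4, 2.7 and 4.0 points.

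**The case against.** - **The plan is silent; it does not reject type.** No primary model is written down, and the reference to baseline sits in a hypothesis. A generous reader might even count type as a baseline value. This is fair as to wording, and the missing model is the wider gap. But in context the phrase points to pretest scores, and nothing in the documents commits to using type in Aim 1.
- **The size is assumed, and the upper cases are strong.** This stands. With equal strata, r = 0.05, 0.10 and 0.15 mean that the types differ by 2√r = 0.45, 0.63 and 0.77 residual SD after baseline adjustment. The treatment effects used in the simulation for those cases are about 0.61, 0.59 and 0.58 SD. From 10% upward, type would have to matter more than treatment. At r = 0.02, on the baseline-only anchor, the loss is only about half a point (80.2% vs 80.8%).
- **Setting the adjusted model at 80% makes the omission look like a shortfall.** On the baseline-only anchor, power never falls below 80%, and the cost is a gain not taken. This is a fair point of framing, but the direction and rough size of the gap do not change.
- **Lack of bias is not unconditional.** This also stands. It holds for randomised data without dropout that depends on both type and arm. The documents describe no dropout pattern. The caveat argues for including type, since likelihood-based handling of missing data can use it only if it is in the model.

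**Conclusion.** The concern holds as a free improvement. The stratification factor is absent from the only description of the Aim 1 comparison, and including it is the better analysis. The omission does not inflate type I error, and it does not bias the estimate unless dropout depends on type and arm together. The cost in power is nil if type adds nothing beyond baseline. It is about 1 to 4 points if type explains 5% to 10% of the remaining variance, and about 4 to 6 points at 15%. These figures assume 80 completers, two-sided alpha 0.05 and equal strata. The documents cannot say where in that range the trial lies, and zero is possible.

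**What to change.** In the Data analysis section, state the Aim 1 model as posttest value = group + baseline value + vulvodynia type (generalized or provoked), fitted by ANCOVA or its FIML equivalent, for the primary outcome and both secondary outcomes.

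The cost is one or two sentences and one degree of freedom. No new data are needed, because type is already established at the screening exam.

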**Title: DOUBLE-BLIND PHASE 2 RCT: EFFECT OF ACUPUNCTURE ON PATIENT VULVODYNIA OUTCOMES**

**RESEARCH PROTOCOL**

Dated 8/15/2017

sham procedure to mask both the acupuncturist and subject to the type of needle used. The acupuncturist will be well-trained in the study protocol and will be observed for fidelity. We will obtain measures at 2 time points (baseline and immediately post 10th acupuncture treatment [5 weeks]). Duration of effects will be measured weekly beginning one week after posttest for up to 12 weeks.

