**Title: DOUBLE-BLIND PHASE 2 RCT: EFFECT OF ACUPUNCTURE ON PATIENT VULVODYNIA OUTCOMES**

**RESEARCH PROTOCOL**

Dated 8/15/2017

however, are regular needles used in routine acupuncture. All participants will be informed that they will receive either real or fake acupuncture and they will not be told what kind of needles they are receiving until they complete the duration of effect portion of the study. Participants in the control group will be offered 10 free real acupuncture sessions with regular (not double-blind) acupuncture needles administered by a second acupuncturist after the end of the 17 weeks. The double blind needles are manufactured by [name], the inventor of the double blind acupuncture needle, and will be sent to us sterilized and packaged to maintain sterility.

All participants will receive 10 acupuncture session, two sessions per week over an approximately 5 week period. Each session will last about one hour. The first and last sessions only, where participants will complete the study questionnaires, are expected to last an additional 30 - 60 minutes. Each acupuncture treatment will consist of 13 acupuncture points, of which 12 points specifically treat problems with the genitals. Once the 13 needles are inserted or placed on the skin in the 13 points, they will remain in place for 45 minutes. The RS will remain with the subjects during the treatment session.

At pre-test, before the first acupuncture session, and at post-test, after the 10th acupuncture treatment, participants will be asked to insert and remove a regular Tampax™ tampon with applicator as a standardized pain stimulus, and will complete the three study measures of vulvar pain and sexual function on a computer or tablet:

- 1) PAINReportIt® computerized program to assess pain intensity as well as collect demographics and medications information
- 2) Female Sexual Function Index (FSFI) to assess dyspareunia and sexual function
- 3) Vulvar Pain Functional Questionnaire to describe the physical dimension of impairment in women with vulvodynia
- 4) At post-test, participants will also complete the Double-Blind Needle Questionnaire for the participants to report whether or not they remained blinded to the type of needle used (penetrating or skin touch placebo).

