Weekly for up to 12 weeks after the 10th treatment session, the subjects will be asked to insert and remove a regular Tampax™ tampon with applicator from their vagina and complete the weekly vulvar pain diary to record their vulvar pain, so that we can determine the duration of the treatment effects.

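### Aim 2 explores duration by arm only among posttest responders, which is not a randomised contrast, and no comparison of all randomised women after posttest is planned (minor; cheap to improve)

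*Combined protocol and SAP*

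**What the plan says.** All references are to the combined protocol and SAP.

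- **Randomisation.** Under Study design, women are stratified by vulvodynia type and "randomized 1:1 either to the penetrating needle group or the skin touch placebo needle group". This happens before any treatment.
- **Aim 1 (Specific aims)** compares the arms at posttest, with baseline adjustment, and goes no further in time.
- **Aim 2 (Specific aims)** begins "In subjects with a clinically meaningful reduction in pain intensity (at least 1.5 points) at posttest compared to pretest, describe the duration", follows those women "weekly until pain returns to pretest or up to 12 weeks after posttest", and intends to "explore the duration of the effect by intervention group, vulvodynia subgroups" and demographic subgroups. Its stated use is to guide later research on initial and maintenance acupuncture.
- **Follow-up.** Study design says: "Duration of effects will be measured weekly beginning one week after posttest for up to 12 weeks". Procedures says that after the tenth session "the subjects will be asked to insert and remove a regular Tampax™ tampon with applicator from their vagina and complete the weekly" pain diary. Neither place restricts the diary to responders.
- **Blinding and control-arm treatment.** Under Procedures, participants will "not be told what kind of needles they are receiving until they complete the duration of effect portion of the study". Control women are offered real sessions "administered by a second acupuncturist after the end of the 17 weeks".
- **Data analysis** gives a general intention-to-treat and FIML statement for missing data, and an exploration of the affective pain score at baseline and after the tenth treatment. It names no analysis of the weekly diary and no between-arm contrast after posttest.

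**The concern.** Response at posttest is a consequence of treatment as well as of the woman's own prognosis and of measurement error. If penetrating needles work, they bring into the responder set women who would not have responded on placebo, while placebo responders are more strongly selected for spontaneous improvement and favourable reading error. The two responder groups can then differ in ways that randomisation had balanced, and a difference between them in later pain mixes treatment effect with selection. The plan does not say this.

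The Background names lack of sham control and lack of follow-up beyond immediate posttest as the gaps in earlier work. A sham-controlled comparison of later pain in everyone randomised would address both together. As written, the plan would report only the responder-conditional contrast, and a reader could take it as the randomised answer on lasting effect.

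**Working it through.** **What the plan fixes.** The only figures that bear on this are the 1.5-point cut-off, 1:1 allocation, 12 weekly diaries, and 80 women with full data (about 40 per arm). The timeline is consistent: 5 weeks of treatment + 12 weeks of diary = 17 weeks, the point after which control women are offered real sessions. No SD, effect size or response rate is given, so everything below is assumed and serves only to show direction and rough size.

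**Model.** True reduction R ~ N(m, b²), with no fading after posttest. Independent reading error of SD e applies at pretest, posttest and each week. A responder has observed drop D ≥ 1.5. Let s = √(b² + 2e²), a = (1.5 − m)/s, λ = φ(a)/(1 − Φ(a)). The share responding is 1 − Φ(a). The mean later reduction from observed pretest among responders is m + [(b² + e²)/s]·λ.

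**Uniform effect** (placebo m = 0.5, penetrating m = 2.0, true difference 1.5). Base case b = e = 1, so s = √3 = 1.732 and (b² + e²)/s = 1.155.
- Penetrating: a = −0.289, response 61.4%, λ = 0.624, mean 2.0 + 1.155 × 0.624 = 2.72.
- Placebo: a = 0.577, response 28.2%, λ = 1.198, mean 0.5 + 1.155 × 1.198 = 1.88.
- Responders-only difference: 2.72 − 1.88 = 0.84, against 1.5 in all women. With 40 per arm, about 25 and 11 women contribute.
- Over nine settings (b and e each 1.0, 1.25, 1.5): 0.74 to 0.92.

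**Effect concentrated in 30% of women** (penetrating: 70% at m = 0.5, 30% at m = 5.5; mean 0.7 × 0.5 + 0.3 × 5.5 = 2.0, so the true difference is again 1.5).
- Without scale limits, the nine settings give 1.81 to 2.19. This overstates the excess, because many women who enter with a score of 4 or more on a 0-10 scale cannot drop 5.5 points.
- With whole-number scores held to 0-10, pretest at least 4 and an assumed baseline of 6.5 (SD 1.25), settings b = e = 1.0, 1.25 and 1.5 give about 2.0, 1.7 and 1.6 in responders. The difference in all women is then about 1.4, 1.4 and 1.3.

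**Common improvers** (20% drop 5 points in both arms; the other 80% drop 1.875 with penetrating needles and 0 with placebo; b = 0). True difference: (0.2 × 5 + 0.8 × 1.875) − (0.2 × 5) = 2.5 − 1.0 = 1.5.
- At e = 1.0, response is 68.2% and 31.4%, and responder means are 3.11 and 3.58, a difference of −0.47.
- At e = 1.25 it is −0.12; at e = 1.5 it is 0.11. Applying the scale limits changes little (about −0.4 to 0.2).

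**A second model**, with persistent individual prognosis (SD 1 to 2), noise SD 1.5 and posttest effects of 1.0 to 1.5 points, gives a week-12 responder contrast 0.20 to 0.59 points too low. With no true week-12 difference it gives −0.20 to −0.58. The comparison of all randomised women recovers the true value to within 0.01.

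**Weeks to return to pretest.** With uniform effects that never fade (base case, cap 12 weeks), simulation gives 10.5 vs 8.5 weeks in responders and 8.3 vs 4.1 in all women. Every modelled gap with an effect favoured penetrating needles.

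**The case against.** The strongest reply is that Aim 2 describes and explores. It states no hypothesis or test, and it lists intervention group beside vulvodynia and demographic subgroups, which are plainly not randomised. The restriction also suits the question: how long an effect lasts has little meaning in a woman who had none at posttest. An analysis of everyone answers a different question, and for weeks to return it would make matters worse, with a gap of 8.3 − 4.1 = 4.2 weeks against 10.5 − 8.5 = 2.0 in responders although nothing fades.

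Most of this stands. It is why the responder description should stay, and why the added comparison should be of weekly pain rather than of time to return. It does not remove the two gaps: exploratory wording does not tell a reader that the arm contrast is non-randomised, and the general intention-to-treat sentence cannot restore women whom Aim 2 excludes by definition.

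Stronger readings that the documents do not support:
- *Aim 2 is invalid, or claims a randomised inference on duration.* It makes no such claim.
- *The duration result could be wrong in either direction.* That was shown for later mean pain only.
- *The sections contradict each other on when the diary ends.* A limit of up to 12 weeks is compatible with an earlier stop when pain returns to pretest. The matter is under-specified, not contradictory.
- *Participant blinding to week 12 is assured.* Disclosure may follow once a woman completes her duration portion. If that can end early, or never starts for non-responders, some may learn their group before week 12.

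**Conclusion.** The point holds as a minor one. The by-arm contrast in Aim 2 is conditional on a post-randomisation outcome, and no comparison of all randomised women after posttest is written down. Under the assumed inputs, a true later difference of about 1.5 points could appear among responders as roughly half to three-fifths of that (uniform effect), as about 0.2 to 0.6 points more than the all-women difference (concentrated effect, scale limits applied), or as about nothing or slightly reversed (common improvers). Neither direction nor size can be predicted from the documents, so the responder contrast should not be read as the randomised effect on later pain. Aim 1 and the descriptive purpose of Aim 2 are untouched.

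**What to change.** 1. Keep the responder description, and label its by-group contrast as descriptive and non-randomised.
2. Add, for all randomised women by assigned group, a repeated-measures comparison of weekly tampon-test pain over the 12 weeks, adjusted for pretest pain and vulvodynia type, using the diary that Procedures already asks subjects to keep.
3. State that all subjects keep the diary for the full 12 weeks or, if it stops when pain returns to pretest, how later weeks are handled.
4. State that participant blinding through week 12 depends on when the duration-of-effect portion ends for each woman.

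Cost: wording and a little more analysis. There are no extra visits, and no extra diaries if all subjects already keep them throughout. The downside is that the all-randomised comparison combines initial response with persistence, so it sits beside the responder description and does not replace it.

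### Aim 2 dates the duration of acupuncture and placebo effects from within-arm falls in pain, but with no untreated arm such durations cannot be separated from fluctuation and regression to the mean

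*Combined protocol and SAP*

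**What the plan says.** Aim 2, in the specific aims, selects its population by an observed change: "In subjects with a clinically meaningful reduction in pain intensity (at least 1.5 points) at posttest compared to pretest". In these women the plan will "describe the duration of the acupuncture treatment and placebo effects weekly until pain returns to pretest or up to 12 weeks after posttest". The follow-up measure is the score after a tampon stimulus: "We will describe the variability over time in vulvar pain intensity (0-10) after a tampon insertion-removal stimulus". The results are to be explored by intervention group, by vulvodynia subgroup and by demographic subgroup, and are meant to inform later research on initial and maintenance acupuncture.

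Under Study design there are only two arms: "we will compare two groups (penetrating acupuncture needle [treatment] group and skin touch needle [placebo] group". Women are "randomized 1:1 either to the penetrating needle group or the skin touch placebo needle group". The same section fixes the occasions that define response, one at baseline and one after the tenth session: "We will obtain measures at 2 time points". Weekly readings start one week after posttest.

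The Data analysis section names intention to treat, full information maximum likelihood for missing data, and an exploratory affective pain score. It gives no method for Aim 2, no test-retest SD and no allowance for regression to the mean.

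**The concern.** A fall from pretest to posttest within one arm is a change, and a change is not in itself an effect. In the skin-touch arm it contains placebo response, the natural course of a fluctuating pain condition, and regression to the mean. The penetrating arm contains the same mixture plus whatever penetration adds. Separating placebo response from the rest needs women who receive no needling. The Background section says that the earlier pilot had a wait-list control; this trial has none.

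Selection adds to the problem. Keeping only women with a fall of 1.5 points favours those whose pretest happened to be high and whose posttest happened to be low. Stopping the clock when pain is back at pretest then turns the undoing of that accident into a number of weeks. Those weeks would be reported as how long acupuncture and placebo last, and used to plan maintenance research.

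**Working it through.** **What the design can identify.** There are two arms, both needled, with response defined by one pretest and one posttest occasion. The randomised contrast identifies the difference between penetrating and skin-touch needles. No contrast identifies needling against nothing, so neither a placebo effect nor its duration can be estimated. Restricting to responders also discards the randomised comparison, because who responds depends on what happened after randomisation.

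**Share of unchanged women who qualify.** The plan states no figure to reproduce. The threshold of 1.5 points comes from Aim 2. The within-woman SD of one reading, s, is not in the documents and is assumed here. For a woman with no true change and independent errors, the observed fall is normal with mean 0 and SD s√2, so

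P(fall ≥ 1.5) = 1 − Φ(1.5 / (s√2)).

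| Assumed s | s√2 | 1.5/(s√2) | P(fall ≥ 1.5) |
|---|---|---|---|
| 0.5 | 0.707 | 2.121 | 1.7% |
| 1.0 | 1.414 | 1.061 | 14.4% |
| 1.5 | 2.121 | 0.707 | 24.0% |
| 2.0 | 2.828 | 0.530 | 29.8% |

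If scores are whole numbers, a fall of 2 is needed; an approximation then gives 15.4%, 24.4% and 30.0% for s = 1.0, 1.5 and 2.0.

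**If the score averages several items.** The primary outcome is "vulvar pain (PAINReportIt® average pain intensity, 0-10", and how the average is formed is not defined. With three items whose errors are independent, s becomes s/√3, and s = 1.0, 1.5 and 2.0 per item give 3.3%, 11.0% and 17.9%. Aim 2 does not say whether the 1.5-point rule uses this score or the tampon-provoked score used in follow-up.

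**What happens to these women afterwards.** Given D ≥ 1.5, with c = 1.5/(s√2), the mean observed fall is s√2 · φ(c)/(1 − Φ(c)). For s = 1.0 this is 1.414 × 0.2273/0.1444 = 2.23 points. Pretest and posttest errors have equal variance, so on average pretest lies 1.11 above the true level and posttest 1.11 below it. For s = 1.5 and 2.0 the half-falls are 1.37 and 1.65. With fresh, independent errors each week, mean pain is back at the true level at week 1 and stays there. A simulation of 1,000,000 women agrees: assuming a true mean of 6, a between-woman SD of 1.5 and no true change, chance responders averaged about 6.3 at weeks 1, 6 and 12 alike. The mean exceeds 6 because entry requires a screening score of 4 or higher.

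**Apparent duration.** Under the same assumptions, the median time to the first weekly score at or above pretest was 5, 4 and 3 weeks for s = 1.0, 1.5 and 2.0 with unrounded scores, and 3, 3 and 2 weeks with whole-number scores. By week 12, 28%, 21% and 16% (unrounded) or 15%, 13% and 11% (whole-number) had not returned. These women have no effect to lose, yet each is given a duration.

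**Entry cutoff.** The Inclusion criteria place the cutoff of 4 on the screening reading, and Procedures describes a pretest tampon stimulus before the first session. With a separate pretest reading, the cutoff leaves the simulated shares essentially unchanged (14.1%, 23.3% and 28.9%, unrounded).

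**The case against.** The strongest reply is that Aim 2 is descriptive. It tests no hypothesis, it reports both arms, and many authors use placebo effect loosely for whatever happens in the placebo arm. The chance component is present in both arms, and a plot of mean pain over time would show an immediate rebound followed by a flat line, which differs from gradual loss of effect. Much of this is fair and limits the seriousness of the point. It does not remove it: describing a quantity does not make it the quantity named, time to first return to pretest hides the flat pattern, and the chance components need not cancel in a comparison of responders only.

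Four stronger readings are tempting, and the documents do not support them.

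- A reader might take some share, such as 14% to 30%, as a property of this trial. The documents give no SD or reliability, so every share above is conditional; a small SD or a multi-item score makes it slight.
- A reader might infer that chance responders drift back slowly, imitating an effect that wears off. Under independent errors the mean rebounds at once and then stays level. Only the first-return times are spread over weeks.
- A reader might infer that the efficacy result is compromised. Aim 1 compares the randomised groups at posttest, controlling for baseline, and does not depend on the responder rule.
- A reader might propose estimating the chance rate from screening and pretest scores. The screening score is selected at 4 or higher, which gives 16%, 28% and 36% in simulation (unrounded) against true rates of 14%, 24% and 30%. It is also a pain-now score, separated from pretest by an unspecified gap, and this comparison covers only women who start at a later visit.

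**Conclusion.** Wrong as written, on one point: this design cannot estimate the duration of a placebo effect, and a within-arm duration in the penetrating group is not the duration of an acupuncture effect. That conclusion follows from the two-arm design and needs no assumed number.

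The size of the chance contribution is uncertain. It is about 2%, 14%, 24% or 30% of women with no true change for an assumed within-woman SD of 0.5, 1.0, 1.5 or 2.0, taking errors as normal and independent between occasions and the score as a single reading. The durations also rest on the assumed true mean and between-woman SD, and on using one scale throughout. The change is worth making because the Aim 2 results are intended to guide later research.

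**What to change.** In Aim 2, replace the duration of acupuncture treatment and placebo effects by the course of pain in each arm among women with a fall of at least 1.5 points, and call no within-arm duration an effect. The same edit should name the pain score to which the 1.5-point rule applies.

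Report the share reaching a 1.5-point fall by arm among all randomised women, and attribute only the between-arm difference to needle penetration. State how women without a posttest score enter that share, since the missing-data statement in the Data analysis section does not address a responder proportion. Do not add a chance benchmark built from screening and pretest scores.

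The cost is a change of wording and one additional table from data already planned; no new arm, visit or measure is needed. The downside is a more modest claim for Aim 2.
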